12.3.2 Analyses of secondary outcome variables

The secondary outcome variables include:

- The proportion (%) of subjects able to self-administer safe and effective injections using the e-Device at Visit 1. Safe and effective self-injection will be evaluated by the HCP and is defined as:
 - Complete Dose Delivery: Subject self-injected the complete dose of CZP as confirmed by a visual inspection of the CZP-cassette(s) which shows the PFS container to be empty and
 - No AEs related to use of the e-Device (ADEs) that would preclude continued use of the e-Device for self-injection.

For subjects on the Q4W dosing regimen who will self-inject twice ($2 \times 200\text{mg CZP}$) at each visit, each injection will be evaluated for safety and effectiveness using the above criteria. The primary endpoint of safe and effective self-injection for subjects on the Q4W dosing regimen will be met only if both self-injections are determined to be safe and effective.

- Percentage of used CZP-cassettes identified as having structural integrity issues based on visual examination (ie, clear evidence of damage/compromised structural integrity, not superficial cosmetic imperfections)

The secondary outcome variables will be summarized using descriptive statistics. All summary statistics will be presented for the FAS overall, by dosing group, and by indication. A subgroup analysis will be performed for subjects in the FAS with impaired hand function.

12.3.3 Analyses of other outcome variables

Other outcome variables are:

- Injection site pain due to self-injection (using a Visual Analog Scale [VAS]; 100mm) by visit at all visits after self-injection using the e-Device
- Responses to the preinjection ASI at Visit 1
- Responses to the postinjection ASI by visit at all visits after self-injection using the e-Device
- In vitro functional evaluation of the e-Device following the final use per subject:
 - The percentage of e-Devices found to be functionally compromised

The other outcome variables will be summarized using descriptive statistics. All other exploratory variables will be summarized for the FAS overall, by dosing group, and by indication.

12.4 Planned safety analyses

12.4.1 Safety analyses

Safety endpoints include AEs and changes from baseline in vital signs. Analyses of the safety data will be done on the SS.

All summaries of continuous safety variables will be presented at scheduled time points. No statistical testing will be conducted on the safety parameters. All AE data will be listed. Only treatment-emergent adverse events (TEAEs) will be included in the summary tables.

Treatment-emergent AEs are defined as AEs starting after the time of first injection in the study up to 70 days after the last self-administration of study medication. All AEs will be coded and classified by system organ class, high level term, and preferred term according to the latest version of the Medical Dictionary for Regulatory Activities (MedDRA®).

In this study, safety reporting requirements apply to all constituents of the IP (including CZP, the e-Device auto-injector, and the CZP-cassette) per 21 CFR 320. Adverse events related to use of the e-Device (ADEs) (including the CZP-cassette) will be summarized separately. Adverse events will be summarized by the frequency and percent of subjects having one or more of the events in question. Planned summaries include overall AEs, AEs by intensity, AEs by relationship to study drug, SAEs, AEs leading to withdrawal, AEs leading to death, ADEs, SADEs, and AEs of special interest.

Physical examination findings will be recorded in the eCRF only at Screening. Clinically relevant changes in subsequent physical examinations will be recorded as AEs.

Physical examination findings at Screening will be listed.

12.5 Handling of protocol deviations

Important protocol deviations are deviations from the protocol which potentially could have a meaningful impact on the primary objective of the study. The criteria for identifying important protocol deviations and the classification of important protocol deviations will be defined within the project Data Cleaning Plan. To the extent feasible the rules for identifying protocol deviations will be defined without review of the data and without consideration of the frequency of occurrence of such deviations. Whenever possible, criteria for identifying important protocol deviations will be implemented algorithmically to ensure consistency in the classification of important protocol deviations across all subjects.

12.6 Handling of dropouts or missing data

There will be no special procedures for handling missing data. All imputation of missing or partial dates for safety assessments will be detailed in the Statistical Analysis Plan.

12.7 Planned interim analysis and data monitoring

No interim analysis is planned.

There will be no Data Monitoring Committee established for this study.

12.8 Determination of sample size

This study will not be powered with respect to any endpoint and sample size is based on practical considerations. The number of subjects and their diagnosed conditions are summarized below.

Approximately 80 subjects who are currently being treated with commercial CZP and are on a stable dosing regimen for at least 3 months will be screened in order to have at least 60 subjects use the e-Device at Visit 1. The 60 subjects using the e-Device at Visit 1 will be composed of a minimum of 15 subjects in each of the dosing groups (Q2W vs Q4W) with a minimum of 15 subjects with CD and a minimum of 10 subjects with impaired hand function. Impaired hand function will be measured using the Cochin scale (Poiraudieu et al, 2000; Duruöz et al, 1996) and impaired hand function will be defined as patients who have a Cochin score ≥ 13.5 at baseline.

13 ETHICS AND REGULATORY REQUIREMENTS

13.1 Informed consent

Subject's informed consent must be obtained and documented in accordance with local regulations, ICH-GCP requirements, and the ethical principles that have their origin in the principles of the Declaration of Helsinki.

Prior to obtaining informed consent, information should be given in a language and at a level of complexity understandable to the subject in both oral and written form by the Investigator (or designee). Each subject will have the opportunity to discuss the study and its alternatives with the Investigator.

Prior to participation in the study, the Informed Consent form should be signed and personally dated by the subject and by the person who conducted the informed consent discussion (Investigator or designee). The subject must receive a copy of the signed and dated Informed

Consent form. As part of the consent process, each subject must consent to direct access to his/her medical records for study-related monitoring, auditing, IRB/IEC review, and regulatory inspection.

If the Informed Consent form is amended during the study, the Investigator (or the Sponsor, if applicable) must follow all applicable regulatory requirements pertaining to the approval of the amended Informed Consent form by the IRB/IEC and use of the amended form.

All studies conducted at centers in the United States must include the use of a Health Insurance Portability and Accountability Act Authorization form.

The subject may withdraw his/her consent to participate in the study at any time. A subject is considered as enrolled in the study when he/she has signed the Informed Consent form. An eCRF must not be started, nor may any study-specific procedure be performed for a given subject, without having obtained his/her written consent to participate in the study.

13.2 Subject identification cards

Upon signing the Informed Consent form, the subject will be provided with a subject identification card in the language of the subject. The Investigator will fill in the subject identifying information and medical emergency contact information. The Investigator will instruct the subject to keep the card with him/her at all times.

13.3 Institutional Review Boards and Independent Ethics Committees

The study will be conducted under the auspices of an IRB/IEC, as defined in local regulations, ICH-GCP, and in accordance with the ethical principles that have their origin in the Declaration of Helsinki.

The Investigator/UCB will ensure that an appropriately constituted IRB/IEC that complies with the requirements of the current ICH-GCP version or applicable country-specific regulations will be responsible for the initial and continuing review and approval of the clinical study. Prior to initiation of the study, the Investigator/UCB will forward copies of the protocol, Informed Consent form, Investigator's Brochure, Investigator's curriculum vitae (if applicable), advertisement (if applicable), and all other subject-related documents to be used for the study to the IRB/IEC for its review and approval.

Before initiating a study, the Investigator will have written and dated full approval from the responsible IRB/IEC for the protocol.

The Investigator will also promptly report to the IRB/IEC all changes in the study, all unanticipated problems involving risks to human subjects or others, and any protocol deviations, to eliminate immediate hazards to subjects.

The Investigator will not make any changes in the study or study conduct without IRB/IEC approval, except where necessary to eliminate apparent immediate hazards to the subjects. For minor changes to a previously approved protocol during the period covered by the original approval, it may be possible for the Investigator to obtain an expedited review by the IRB/IEC as allowed.

As part of the IRB/IEC requirements for continuing review of approved studies, the Investigator will be responsible for submitting periodic progress reports to the IRB/IEC (based on IRB/IEC requirements), at intervals appropriate to the degree of subject risk involved, but no less than once per year. The Investigator should provide a final report to the IRB/IEC following study completion.

UCB (or its representative) will communicate safety information to the appropriate regulatory authorities and all active Investigators in accordance with applicable regulatory requirements. The appropriate IRB/IEC will also be informed by the Investigator or the Sponsor, as specified by the applicable regulatory requirements in each concerned country. Where applicable, Investigators are to provide the Sponsor (or its representative) with evidence of such IRB/IEC notification.

13.4 Subject privacy

UCB staff (or designee) will affirm and uphold the subject's confidentiality. Throughout this study, all data forwarded to UCB (or designee) will be identified only by the subject number assigned at Screening.

The Investigator agrees that representatives of UCB, its designee, representatives of the relevant IRB/IEC, or representatives of regulatory authorities will be allowed to review that portion of the subject's primary medical records that directly concerns this study (including, but not limited to, laboratory test result reports, ECG reports, admission/discharge summaries for hospital admissions occurring during a subject's study participation, and autopsy reports for deaths occurring during the study).

13.5 Protocol amendments

Protocol changes may affect the legal and ethical status of the study and may also affect the statistical evaluations of sample size and the likelihood of the study fulfilling its primary objective.

Significant changes to the protocol will only be made as an amendment to the protocol and must be approved by UCB, the IRB/IEC, and the regulatory authorities (if required), prior to being implemented.

14 FINANCE, INSURANCE, AND PUBLICATION

Insurance coverage will be handled according to local requirements.

Finance, insurance, and publication rights are addressed in the Investigator and/or CRO agreements, as applicable.

16 APPENDICES

16.1 Injection Site Pain (VAS)

This scale should be completed immediately postinjection (within 15 minutes).

Injection site pain due to self-injection immediately (within 15 minutes) after injection

Please mark a vertical line on the scale below to show how much pain you experience at the injection site right now

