3.3 Other objectives

The other objectives are to evaluate:

- The functional status of the e-Device following administration of the final study dose (ie, no visual signs of damage, device functions normally with training cassette)
- Subject experience of self-injection as assessed by the Pain Visual Analog Scale (VAS) and Assessment of Self Injection (ASI).
- Subject preference for e-Device vs PFS using a self-administered Self-Injection Preference Questionnaire

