4.1.3 Other outcome variables

The other outcome variables are:

- Injection site pain due to self-injection (using a VAS; 100mm) by visit at all visits after self-injection using the e-Device

Subjects on the Q4W dosing regimen who will self-inject twice (2×200mg CZP) at each visit will complete the Pain VAS after the second injection at each of the 2 visits. For subjects on the Q4W dosing regimen, the Pain VAS will record the overall pain associated with both self-injections.

- Responses to the preinjection ASI at Visit 1
- Responses to the postinjection ASI by visit at all visits after self-injection using the e-Device

Subjects on the Q4W dosing regimen who will self-inject twice (2×200mg CZP) at each visit will complete the postinjection ASI after the second injection at each of the 2 visits. For subjects on the Q4W dosing regimen, the postinjection ASI will collect the overall self-injection experience associated with both self-injections.

- Responses to the Self-Injection Preference Questionnaire
- In vitro functional evaluation of the e-Device following the final use per subject:
 - The percentage of e-Devices found to be functionally compromised (ie, visual signs of damage, device does not function normally with training cassette)

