7.2 Treatment to be administered

The treatments are summarized in [Table 7-1](#).

Table 7-1: Treatments to be administered

Delivery system	Reusable e-Device with single-use cassette
Manufacturer	UCB
Content	Loaded with a single-use cassette that houses a PFS containing 200mg/mL, 1mL of CZP liquid formulation in 10mM sodium acetate, 125mM sodium chloride pH 4.7

CZP=certolizumab pegol; PFS=pre-filled syringe

Each dose will be administered as sc injections in either the right or left lateral abdominal wall or the right or left thigh. Treatment of the injection site with an anesthetic cream prior to dosing is not permitted.

Each injection should be administered at a separate injection site, and rotation between the injection sites should be observed.

At Visit 1 and Visit 2, Q2W group subjects will self-inject CZP 200mg (1×200mg injection) using the e-Device. At Visit 1 and Visit 2, Q4W group subjects will self-inject CZP 400mg (2×200mg injections) using the e-Device.

Before injection, the CZP-cassette should be brought to room temperature by removing from the refrigerator and placing on a table at room temperature for 30 to 45 minutes. Subjects will be observed onsite for 30 minutes after self-injection with CZP using the e-Device for any AEs. Subjects will be asked to contact the designated site personnel in case any AEs occur outside of the site visits.

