9 ASSESSMENT OF SELF-INJECTION

9.1 Injection Site Pain (VAS)

A VAS will be used to assess overall injection pain due to self-injection postinjection at every visit during the Study Treatment Period. Subjects will be required to indicate their injection pain by placing a mark on a 100mm line from 0 (no pain) to 100 (worst possible pain). The VAS will be assessed immediately postinjection (within 15 minutes). The subject will complete the VAS prior to completion of the postinjection ASI.

Subjects on the Q4W dosing regimen who will self-inject twice (2×200mg CZP) at each visit will complete the Pain VAS after the second injection at each of the 2 visits. For subjects on the Q4W dosing regimen, the Pain VAS will record the overall pain associated with both self-injections.

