9.2 Assessment of Self Injection (ASI)

The preinjection ASI is composed of 6 items grouped into 2 domains. The postinjection ASI is composed of 44 items grouped into 6 domains. The domains are feeling about injections, self-image, self-confidence, pain and skin reactions during and after injections, ease of use of the self-injection device, and satisfaction with self-injection.

The preinjection ASI will be completed preinjection at Visit 1, and the postinjection will be completed within 30 minutes postinjection at each visit during the Study Treatment Period. The ASI has been developed from the Self-Injection Assessment Questionnaire and modified to reflect the improved features of the e-Device and is being piloted in this study. It will be validated using a separate psychometric analysis plan.

Subjects on the Q4W dosing regimen who will self-inject twice (2×200mg CZP) at each visit will complete the postinjection ASI after the second injection at each of the 2 visits. For subjects on the Q4W dosing regimen, the postinjection ASI will collect the overall self-injection associated with both self-injections.

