b. Giving yourself an injection in a clean and sterile way?	1	2	3	4	5
c. Giving yourself an injection safely?	1	2	3	4	5

THANK YOU FOR COMPLETING THIS QUESTIONNAIRE

Assessment of Self-Injection (ASI) [and draft new items] POST-Self-Injection

Introduction

The following questions concern the self-injection of your medication and must be answered after giving yourself an injection **using the [prefilled syringe / AutoClicks prefilled pen / ava®]**.

Thank you for completing this questionnaire by yourself, preferably in a quiet environment. Take as much time as you need to complete it. There are no right or wrong answers. Your answers will remain strictly confidential and anonymous.

FEELINGS ABOUT INJECTIONS

The following questions concern your **feelings about injections**.

Please answer each question below by circling the number that best represents your opinion (circle only one number per question).

1. In general, how afraid are you of needles?

Not at all 1	A little 2	Moderately 3	Very 3	Extremely 4
-----------------	---------------	-----------------	-----------	----------------

2. In general, how afraid are you of having an injection?

Not at all 1	A little 2	Moderately 3	Very 4	Extremely 5
-----------------	---------------	-----------------	-----------	----------------

3. How anxious do you feel about giving yourself an injection?

Not at all 1	A little 2	Moderately 3	Very 4	Extremely 5
-----------------	---------------	-----------------	-----------	----------------

SELF-IMAGE

The following questions concerns **your self-image when using the [prefilled syringe / AutoClicks prefilled pen / ava®]**.

Please answer the questions below by circling the number that best represents your opinion (circle only one number per question).

4. How self-conscious would you feel about using the prefilled syringe / AutoClicks prefilled pen / ava®...	Not at all	A little	Moderately	Very	Extremely
a. ... around your family ?	1	2	3	4	5
b. ... around your friends ?	1	2	3	4	5
c. ... around people you don't know ?	1	2	3	4	5

This document cannot be used to support any marketing authorization application and any extensions or variations thereof.
REDACTED COPY

SELF-CONFIDENCE

The following questions concern your **confidence** about giving yourself an injection **using the [prefilled syringe / AutoClicks prefilled pen / ava®]**.

Please answer each question below by circling the number that best represents your opinion (circle only one number per question).

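### Two printed questionnaire forms do not match the descriptive outcomes they feed: the single pain VAS asks for current pain at one site, and post-injection ASI item 1 is numbered 1-2-3-3-4

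*Protocol*

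**What the plan says.** **Pain VAS.** Protocol 3.3 lists as an objective "Subject experience of self-injection as assessed by the Pain Visual Analog Scale (VAS) and Assessment of Self Injection (ASI"). Protocol 9.1 introduces the VAS as a measure of overall injection pain from self-injection, at every treatment visit and for all subjects. Protocol 4.1.3 adds that Q4W subjects "will complete the Pain VAS after the second injection at each of the 2 visits", and Protocol 9.1 and SAP 8.3.1 state that for them "the Pain VAS will record the overall pain associated with both self-injections". On the two Q4W injections, Protocol 7.2 says: "Each injection should be administered at a separate injection site". The only form printed, in Protocol 16.1, asks the subject to "show how much pain you experience at the injection site right now". There is no separate Q4W version.

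**ASI.** Protocol 16.2 asks subjects to answer by circling a number. Post-injection item 1 (fear of needles) is printed *Not at all* 1, *A little* 2, *Moderately* 3, *Very* 3, *Extremely* 4. The same question in the pre-injection module, and post-injection items 2 and 3, run 1 to 5. SAP 8.3.3 takes the domain score as the mean of its item scores, provided at least half of the items are answered. It does not say whether an item score is the printed digit or the verbal label. The appendix heading carries the words "and draft new items", the text still has an unresolved device choice ("using the [prefilled syringe / AutoClicks prefilled pen / ava"), and Protocol 9.2 says that the instrument has been "modified to reflect the improved features of the e-Device and is being piloted in this study".

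**The concern.** In both cases the form a subject fills in and the quantity the SAP will report are not the same thing.

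For the VAS, the gap has two parts. The form asks about the present moment and the variable about the injection experience as a whole; this applies to both dosing groups. The form also refers to one site, while a Q4W subject has two; this applies to Q4W only. A table headed as overall pain of both injections could then report answers to a different question.

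For the ASI, two adjacent answers share a code and the top answer is one point short. If the digit is what reaches the database, fear of needles after use of the device is recorded too low for anyone who answers *Very* or *Extremely*. The same domain is also summarised before injection on an intact 1 to 5 scale, so the two sets of values would not be on one scale. Protocol 16.2 has staff check the questionnaire for completeness only and not query answers, so routine review would not pick this up.

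**Working it through.** **(a) VAS: texts side by side.** No arithmetic applies.

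| Feature | Form (Protocol 16.1) | Variable, all subjects (Protocol 9.1) | Variable, Q4W (Protocol 4.1.3, 9.1; SAP 8.3.1) |
|---|---|---|---|
| Time | present moment, within 15 minutes | overall injection pain | overall pain, rated once after the second injection |
| Site | one | not specified | both injections, at separate sites (Protocol 7.2) |

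The 15-minute window agrees throughout. Time frame differs for both groups; site differs for Q4W. The documents hold no data on how pain fades, on the interval between the two Q4W injections, or on how subjects read the question, so neither size nor direction can be worked out.

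**(b) ASI item 1.**

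*Check of the text.* Post-injection items as printed, by domain: 3 + 3 + 3 + 10 + 17 + 8 = 44, in 6 domains. This reproduces the total in Protocol 9.2 and SAP 8.3.3, so no item has been lost. One of the 44 has the irregular numbering; the other 43 run 1 to 5 or 1 to 6.

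*Inputs.* The feelings-about-injections domain has 3 items. Printed codes for item 1 are 1, 2, 3, 3, 4; expected codes are 1, 2, 3, 4, 5. At least half of 3 items means at least 2.

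*Effect on one subject, if the printed digit is captured.* The error on item 1 is 0 for the three lower answers and −1 for *Very* (3 instead of 4) and *Extremely* (4 instead of 5). The domain shift is the error divided by the number of items answered.

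| Items answered | Shift for *Very* or *Extremely* | Highest possible domain score |
|---|---|---|
| all 3 | −1/3 = −0.33 | (4 + 5 + 5)/3 = 4.67, not 5 |
| item 1 and one other | −1/2 = −0.50 | (4 + 5)/2 = 4.50, not 5 |
| items 2 and 3 only | 0 | 5 |

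*Effect on a group mean.* With all items answered, shift = −(share answering *Very* or *Extremely*)/3. The documents do not give this share, so the following are assumptions only: 5% gives −0.05/3 = −0.02; 20% gives −0.20/3 = −0.07; 50% gives −0.50/3 = −0.17. All subjects have self-injected for at least 3 months (Protocol 6.1, criterion 6), which makes the low end more plausible but does not fix a figure.

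*If the label or position is coded.* The shift is 0 for everyone.

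**The case against.** **VAS.** The form's heading speaks of pain due to self-injection and uses the same 15-minute window as the protocol text. A rating given after the second injection may well take in both sites, and site staff may explain this. The line and its anchors are not in the available text, so a further instruction on the form cannot be excluded. All of this stands, and it limits the point to a mismatch of wording. A reader might infer that Q4W pain will be understated. The documents do not support that, since nothing in them gives a direction. A reader might also infer that only Q4W subjects need a new form. That does not follow either: one form serves everyone, and Protocol 9.1 uses the overall wording for Q2W as well.

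**ASI.** The appendix is visibly a draft template, and the table was read from PDF. Protocol 9.2 refers to a separate psychometric analysis plan, which may define item coding. On paper the two 3s sit under different labels, so the position of the circle still identifies the answer. These points stand as well, and they make the harm conditional. A fault in text reading looks unlikely, because the labels are intact and the neighbouring items read correctly, but it cannot be ruled out. A reader might infer that the reported ASI scores will be wrong, or that a pre-to-post comparison is biased in favour of the device. The documents show neither: how the eCRF codes item 1 is not stated, and no change score or test is planned for the ASI.

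**Conclusion.** The point holds in a limited form. Both mismatches are in current text and both instruments serve a stated objective, but only descriptive other outcomes are affected. The primary, secondary and safety outcomes do not depend on either form. Severity is low.

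(a) The single VAS form and the stated variable differ in time frame for all subjects and also in site for Q4W. No size or direction can be given.

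(b) The ASI effect rests on one assumption, that the printed digit is captured. If so, each subject answering *Very* or *Extremely* to item 1 loses 0.33 on that domain, or 0.50 with only item 1 and one other item answered. The pre- and post-injection scores for that domain are then on different scales. If coding is by label, or the fielded form already runs 1 to 5, there is no effect.

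**What to change.** **(a) VAS.** Reconcile the one form with the one variable, for all subjects, by either route:

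- If no forms have been completed, reword the question to ask for overall pain from the self-injection or self-injections at this visit. This costs one line on the form.
- If forms have been completed, keep the wording and relabel the outcome in SAP 8.3.1 as current injection-site pain after the last injection of the visit. Record this in SAP 3.9, which at present lists no changes to protocol-defined analyses. This costs a few words and avoids two versions that cannot be compared.

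Do not create a Q4W-only version. SAP 8.3.1 has an overall row, which would then pool two different questions. RA, PsA and AS occur in both dosing groups, so any row for these indications taken across the groups would do the same.

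**(b) ASI.** Print *Very* 4 and *Extremely* 5 in post-injection item 1. Confirm that the fielded form and the eCRF codelist use 1 to 5. Add one sentence to SAP 8.3.3 saying that item 1 is scored 1 to 5 by verbal label or position, not by the printed digit. For any completed paper forms with the misprint, the position of the circle allows the answer to be recovered. The cost is two digits, one check and one sentence.
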